8.1.2 Suspected Adverse Reaction

Suspected adverse reaction means any adverse event for which there is a reasonable possibility that the drug caused the adverse event. The term 'reasonable possibility' means there is evidence to suggest a causal relationship between the drug and the adverse event. A suspected adverse reaction implies a lesser degree of certainty about causality than adverse reaction, which means any adverse event caused by a drug.

8.1.3 Unexpected Adverse Reaction

An adverse event or suspected adverse reaction is considered "unexpected" if it is not listed in the investigator brochure or is not listed at the specificity or severity that has been observed; or, if an investigator brochure is not required or available, is not consistent with the risk information described in the general investigational plan or elsewhere in the current application. "Unexpected", also refers to adverse events or suspected adverse reactions that are mentioned in the investigator

brochure as occurring with a class of drugs or as anticipated from the pharmacological properties of the drug, but are not specifically mentioned as occurring with the particular drug under investigation.

8.1.4 Serious Adverse Events

An adverse event or suspected adverse reaction is considered serious if in the view of the investigator or the sponsor*, it results in any of the following:

- Death.
- A life-threatening adverse drug experience.
- NOTE: The term “life-threatening” in this definition refers to an event in which the subject is at risk of death at the time of the event; it does not refer to an event that hypothetically might cause death if it were more severe.
- Inpatient hospitalization or prolongation of existing hospitalization, excluding hospitalizations done to facilitate research studies or for non-medical reasons (to facilitate completion of protocol-directed requirements, i.e. biopsy, imaging, desensitization for platinum).
- Persistent or significant incapacity or substantial disruption of the ability to conduct normal life functions.
- A congenital anomaly/birth defect.
- Important medical events that may not result in death, be life-threatening, or require hospitalization may be considered a serious adverse drug experience when, based upon appropriate medical judgment, they may jeopardize the patient or subject and may require medical or surgical intervention to prevent one of the outcomes listed in this definition. Examples of such events include, but are not limited to, intensive treatment in an emergency room or at home for allergic bronchospasm; blood dyscrasias or convulsions that do not result in hospitalization.
- Potential drug induced liver injury (DILI)**
- Suspected transmission of an infectious agent (e.g. pathogenic or nonpathogenic) via the study drug is a serious adverse event.

*[name] is the sponsor of this trial.

****Potential Drug Induced Liver Injury**

Wherever possible, timely confirmation of initial liver-related laboratory abnormalities should occur prior to the reporting of a potential DILI event. All occurrences of potential DILIs, meeting the defined criteria, must be reported as potential drug induced liver injury is defined as:

1) ALT or AST elevation > 3 times upper limit of normal (ULN)

AND

2) Total bilirubin > 2 times ULN, without initial findings of cholestasis (elevated serum alkaline phosphatase)

AND

3) No other immediately apparent possible causes of AST/ALT elevation and hyperbilirubinemia, including, but not limited to, viral hepatitis, pre-existing chronic or acute liver disease, or the administration of other drug(s) known to be hepatotoxic.

8.1.5 Severity of Adverse Events

All non-hematologic adverse events will be graded according to the NCI Common Terminology Criteria for Adverse Events (CTCAE) version 4.0. The CTCAE v4.0 is available at <http://ctep.cancer.gov/reporting/ctc.html>

Attribution categories are as follows:

- Definite – The AE *is clearly related* to the study treatment.
- Probable – The AE *is likely related* to the study treatment.
- Possible – The AE *may be related* to the study treatment.
- Unlikely – The AE *is doubtfully related* to the study treatment.
- Unrelated – The AE *is clearly NOT related* to the study treatment.

8.2 Adverse Event Monitoring

Adverse event data collection and reporting, which are required as part of every clinical trial, are done to ensure the safety of Subjects enrolled in the studies as well as those who will enroll in future studies using similar agents. Adverse events are reported in a routine manner at scheduled times during a trial. Additionally, certain adverse events must be reported in an expedited manner to allow for optimal monitoring of patient safety and care.

8.3 Reporting Requirements for Adverse Events

Participating investigators (all sites) must report all serious adverse events to the Sponsor-Investigator within **24 hours** of discovery or notification of the event. The participating investigator must also provide follow-up information on the SAE until final resolution. The Sponsor-Investigator can be contacted at [name], E-mail: [contact], [contact] with CC to [contact] and CC to sub-investigator [name], E-mail: [contact].

The Sponsor-Investigator will review the SAE and report the event to the FDA, external collaborator(s), IND manufacturer, and IRB as applicable as described below.

It is the Sponsor-Investigator's responsibility (e.g. lead site PI) to ensure that all serious adverse events that occur on the study (e.g. all SAEs that occur at each enrolling institution) are reported to all participating sites.

*After informed consent has been obtained but prior to initiation of study treatment, only serious adverse events caused by a protocol-mandated intervention (e.g., invasive procedures such as biopsies) should be reported.

**After initiation of study treatment, all adverse events will be reported until 30 days after the last dose of study treatment or last observation follow-up visit or until initiation of new systemic anti-cancer therapy, whichever occurs first, and serious adverse events will continue to be reported until 90 days after the last dose of study treatment or last observation follow-up visit or until initiation of new systemic anti-cancer therapy, whichever occurs first.

8.3.1 Expedited IRB Reporting

The institutional officials must be notified within 10 business days of “any unanticipated problems involving risk to subjects or others” (UPR). UPRs are defined as any problem or event that is considered: 1) serious, 2) unexpected, and 3) at least possibly related to study participation.

8.3.2 FDA Reporting Criteria

8.3.2.1 IND Safety Reports to the FDA (Refer to 21 CFR 312.32)

The Sponsor will notify the FDA of any unexpected fatal or life-threatening suspected adverse reactions as soon as possible but no later than 7 calendar days of initial receipt of the information using the MedWatch Form 3500a.

The Sponsor is also responsible for reporting any:

- suspected adverse reaction that is both serious and unexpected
- any findings from clinical, epidemiological, or pooled analysis of multiple studies or any findings from animal or in vitro testing that suggest a significant risk in humans exposed to the drug
- clinically important increase in the rate of a serious suspected adverse reaction over that listed in the protocol or investigator brochure

to the FDA and to all investigators no later than 15 calendar days after determining that the information qualifies for reporting using the MedWatch Form 3500a. If FDA requests any additional data or information, the sponsor must submit it to the FDA as soon as possible, but no later than 15 calendar days after receiving the request.

SAEs should be reported on MedWatch Form 3500A, which can be accessed at:

<http://www.accessdata.fda.gov/scripts/medwatch/>

MedWatch SAE forms should be sent to the FDA at:

MEDWATCH

[name]

[name]

Fax: [name] ([name])

<http://www.accessdata.fda.gov/scripts/medwatch/>

8.3.2.2 FDA Annual Reports (Refer to 21 CFR 312.32)

The study Sponsor will submit a brief report annually of the progress of the trial within 60 days of the anniversary date that the IND went into effect as indicated in 21CFR 312.33, and any associated FDA correspondences regarding the IND annual report.

8.3.3 IND Manufacturer Reporting

8.3.3.1 Reporting of Adverse Events (SAEs) to Advanced Accelerator Applications (AAA)

A copy of the MedWatch/AdEERs report must be faxed to AAA at the time the event is reported to the FDA. It is the responsibility of the investigator to compile all necessary information and ensure that the FDA receives a report according to the FDA reporting requirement timelines and to ensure that these reports are also submitted to AAA at the same time.

* Send SAE report and accompanying cover page by way of email to [contact] (email is the preferred method)

OR

* Send SAE report and accompanying cover page by way of fax to line: [name]

8.3.3.2 Reporting of Adverse Events (SAEs) to Bristol-Myers Squibb (BMS)

See Appendix E for mandatory adverse event reporting information. All serious adverse events must be reported to BMS Worldwide Safety.

9.0 DRUG INFORMATION

9.1 ¹⁷⁷Lu-DOTA⁰-Tyr³-Octreotate

9.1.1 Investigational Drug Product: ¹⁷⁷Lu-DOTA⁰-Tyr³-Octreotate

¹⁷⁷Lu-DOTA⁰-Tyr³-Octreotate is a radiopharmaceutical solution for infusion supplied as a ready-to-use product. No manipulation of the product is needed at the clinical site. The only Quality Control (QC) tests that must be performed at the clinical site are; 1) confirm correct product certificate; 2) determine total radioactivity; 3) confirm visual appearance. Since ¹⁷⁷Lu-DOTA⁰-Tyr³-Octreotate is manufactured in centralized GMP facilities, the majority of required QC tests are performed before product shipment. A batch release certificate of the product will be sent to the investigational centers. This batch release certificate is provided by the Qualified Person (QP) of the manufacturing site to ensure that the product is suitable for administration and that it meets the specifications indicated in the Investigational Medicinal Product Dossier (IMPD).

The product is manufactured and supplied to the clinical sites in monodose vials. One vial, for one administration, contains 3.7 GBq (100 mCi) or 7.4 GBq (200 mCi) of ¹⁷⁷Lu-DOTA⁰-Tyr³-Octreotate at calibration time (the time of infusion). The variability of the volume depends on the time between the calibration date and the production date. The product will be shipped and calibrated for use at 24h or 48h after production in a centralized GMP facility. The calibration time of a dose depends on the distance from the manufacturing facility to the clinical sites. The amount

of administered radioactivity is specified at the time of infusion. Additional information on recommendations for treated patients are provided in Appendix F.

Chemical-physical properties of each dose are listed in the Table 10.

Table 9. ¹⁷⁷Lu-DOTA⁰-Tyr³-Octreotate Infusion Solution Composition.

Component	Composition (one vial)	Function
¹⁷⁷ Lu-DOTA ⁰ -Tyr ³ -Octreotate	7.4 GBq / 200 mCi	Active Pharmaceutical Ingredient
X-DOTA ⁰ -Tyr ³ -Octreotate	█ μg/mL	Total peptide content
¹⁷⁷ Lu-DOTA ⁰ -Tyr ³ -Octreotate	█ μg/mL*	Active Pharmaceutical Ingredient
DOTA ⁰ -Tyr ³ -Octreotate	█ μg/mL*	Active Pharmaceutical Ingredient Precursor
Volume	From 22-25 mL	
Specific Activity (GBq/Total peptide)	█ GBq/μmol (at EOP)*	
Radioconcentration	370 MBq/mL (at EOP)	
Other Constituents/Excipients	mg/mL	
█	█	pH adjuster
█	█	█
█	█	Radiation Stability Enhancer
█	█	█
█	█	Masking Agent
█	█	Blood isotonic solution
Water for Injection	-	Solvent

*Values calculated assuming ¹⁷⁷Lu specific activity of 740 GBq/mg at labelling time and a mean synthesis yield of █ and radiochemical purity █

Treatment with ¹⁷⁷Lu-DOTA⁰-Tyr³-Octreotate will consist of a cumulative dose of 14.8 GBq (400 mCi) or 29.6 GBq (800mCi) with the dosing equally divided among 4 administrations of ¹⁷⁷Lu-DOTA⁰-Tyr³-Octreotate at 8±1-weeks intervals.

9.1.2 Handling

¹⁷⁷Lu-DOTA⁰-Tyr³-Octreotate must be administered at the investigational site. The study medication must be stored, handled and administered only by qualified/authorized personnel and must be prepared in accordance with pharmaceutical quality requirements, and radiation safety regulations for ¹⁷⁷Lu-DOTA⁰-Tyr³-Octreotate.

9.1.3 Packing and Labeling

¹⁷⁷Lu-DOTA⁰-Tyr³-Octreotate will be prepared, packaged, labelled, and released under the responsibility of Advanced Accelerated Application's Standard Operating Procedures (SOPs), Good Manufacturing Practice (GMP) guidelines, ICH Good Clinical Practice (GCP) guidelines, and applicable local laws/regulations. Instructions for shipment, storage and handling of the ¹⁷⁷Lu-DOTA⁰-Tyr³-Octreotate Solution of Infusion are provided in Appendix G.

9.1.4 Destruction

The used/unused medications, except for ¹⁷⁷Lu-DOTA⁰-Tyr³-Octreotate, which will be locally discarded, will be returned to the proper local depot for destruction at the study completion or upon expiration, according to IPM/Sponsor decision and approval.

9.2 Nivolumab

9.2.1 Description

Product name	Nivolumab Injection, 100 mg/vial (10 mg/mL)
Product description and Packaging	Packaging: Vials assembled into dispensing boxes containing 5 vials of 100 mg Nivolumab Vials: 10 cc Type I glass vial, 20 mm stopper and seal Appearance: Clear to opalescent, colorless to pale yellow liquid, light (few) particulates may be present.
Product Ingredients	Each vial contains Nivolumab 100 mg active

9.2.2 Handling and Dose preparation

As with all injectable drugs, care should be taken when handling and preparing nivolumab. Whenever possible, nivolumab infusions should be prepared in a laminar flow hood, glovebox, or safety cabinet using standard procedures for the safe handling of intravenous agents applying aseptic techniques. Gloves are required. If nivolumab solution comes in contact with the skin or mucosa, immediately and thoroughly wash with soap and water.

9.2.3 Dose Preparation and administration

Visually inspect drug product solution for particulate matter and discoloration prior to administration. Nivolumab is a clear to opalescent, colorless to pale-yellow solution. Discard the vial if the solution is cloudy, discolored, or contains extraneous particulate matter other than a few translucent-to-white, proteinaceous particles. Do not shake the vial.

Preparation

- Withdraw the required volume of nivolumab and transfer into an intravenous container.

- Dilute nivolumab with either 0.9% Sodium Chloride Injection, USP or 5% Dextrose Injection, USP to prepare an infusion with a final concentration ranging from 1 mg/mL to 10 mg/mL. For dilution, nivolumab injection may either be added to an empty infusion container and then further diluted by addition of NS or D5W, or the nivolumab injection may be added directly to an appropriate volume of NS or D5W in a pre-filled infusion container.
- Mix diluted solution by gentle inversion. Do not shake.
- Discard partially used vials or empty vials of nivolumab according to protocol section 9.2.4.

Storage of Infusion

The product does not contain a preservative. After preparation, store the nivolumab infusion either:

- at room temperature for no more than 4 hours from the time of preparation. This includes room temperature storage of the infusion in the IV container and time for administration of the infusion

OR

- under refrigeration at 2°C to 8°C (36°F to 46°F) for no more than 24 hours from the time of infusion preparation.

Do not freeze.

9.2.4 Study Drug Destruction

Study drugs (those supplied by BMS or sourced by the site/investigator) can be destroyed on site if local policies allow to do so. It is the Investigator's responsibility to ensure that arrangements have been made for the disposal, procedures for proper disposal have been established according to applicable regulations, guidelines and institutional procedures, and appropriate records of the disposal have been documented. The unused study drugs can only be destroyed following BMS approval and after being inspected and reconciled by the responsible site manager (SMN). If required by local country/hospital regulations drug can be returned to an off-site drug destruction vendor, but should only be completed with your SMN while they are on site. All drug destruction whether performed on or off site should be documented using the Investigational Product Return Form or local form as provided by SMN.

10.0 CORRELATIVES/SPECIAL STUDIES

Contribution to correlative studies by each site is recommended and encouraged by the Sponsor, but is optional for the participating sites.

10.1 Pathology correlative studies

PD-L1 protein expression in pretreatment tumor biopsy samples will be evaluated using a validated automated immunohistochemistry (IHC) assay (Dako, Carpinteria, CA, USA) that uses a rabbit monoclonal PD-L1 antibody (clone 28-8; Epitomics Inc, Burlingame, CA, USA). We will assess whether PD-L1 expression is associated with the clinical outcome following administration of ¹⁷⁷Lu-DOTA⁰-Tyr³-Octreotate and nivolumab. PD-L1 expression will be categorized as positive

if $\geq 1\%$ of tumor cells in a section that includes ≥ 100 evaluable tumor cells display PD-L1. Different cut-off values will also be assessed retrospectively.

Acknowledging the difficulties in obtaining fresh tumor samples in SCLC, utilization of archival tumor material will be allowed. Optional tumor biopsies from consenting patients will also be performed at the following times.

- Prior to treatment
- At the time of progression

If sufficient material is available, in addition to PD-L1, other biomarkers in the tumor and stromal compartments including SSTR2, TIM-3, VISTA, FOXP3, LAG3, and IDO-1 may be analyzed. Expression of downstream signaling molecules of SSTR2 (e.g. AKT, MYC) may also be investigated.

Each patient sample set will be assigned a unique patient identifier. The protocol scientific investigator(s) handling the samples will be blinded as to the patient identification, patient data and outcome.

10.2 Specimen Banking

Patient samples collected at Georgetown University and sent from an outside institution will be retained in the [name] lab.

[name]., Ph.D.

[name]

Georgetown University

[name]

Specimens will be stored indefinitely or until they are used up. If future use is denied or withdrawn by the patient, best efforts will be made to stop any additional studies and to destroy the specimens.

Dr. [name] will be responsible for reviewing and approving requests for clinical specimen from potential research collaborators outside of Georgetown University Medical Center.

Collaborators will be required to complete an agreement (a Material Transfer Agreement or recharge agreement) that states specimens will only be released for use in disclosed research.

The following information obtained from the subject's medical record may be provided to research collaborators when specimens are made available:

- Diagnosis
- Collection time in relation to study treatment
- Clinical outcome – if available
- Demographic data

11.0 STATISTICAL CONSIDERATIONS

11.1 Study Design

This is a phase I/II clinical trial of $^{177}\text{Lu-DOTA}^0\text{-Tyr}^3\text{-Octreotate}$ and nivolumab, in patients with ES-SCLC. The primary endpoint of the phase I portion is to determine the recommended phase II doses of $^{177}\text{Lu-DOTA}^0\text{-Tyr}^3\text{-Octreotate}$ when given in combination with nivolumab. Patients with relapsed or refractory ES-SCLC and patients with advanced or inoperable grade I-II pulmonary NETs are also eligible for the phase I portion. For all patients participating in this phase I/II study, a positive SRI (Somatostatin Receptor Imaging) scan showing overexpression of SSTR2 will be mandatory for inclusion (NETSPOT®). The phase II portion will consist of patients with ES-SCLC that completed standard first-line chemotherapy with a platinum-based regimen, without disease progression (responders plus stable disease) at the time of initiation the combination therapy with $^{177}\text{Lu-DOTA}^0\text{-Tyr}^3\text{-Octreotate}$ and nivolumab. Patients will be randomly allocated in two arms: one will be treated with the combination of $^{177}\text{Lu-DOTA}^0\text{-Tyr}^3\text{-Octreotate}$ and nivolumab, and the other arm will continue be followed (observation) after completion the standard chemotherapy treatment. Cross-over will be permitted at the time of disease progression.

11.2 Sample Size and Accrual

ES-SCLC (i.e. SCLC that has spread beyond the supraclavicular areas or with distant metastases) remains incurable with current management options, and patients are treated with combination chemotherapy. Several chemotherapy combinations are active in SCLC, but usually a platinum-containing regimen is chosen. The ORR of platinum-based therapy administered to patients with ES-SCLC ranges from 40 to 80%, and the median PFS ranges from 5 to 7 months in patient series treated in a clinical trial setting (phase-II/III studies) [9, 10, 48-55]. A placebo-controlled randomized phase II study of maintenance sunitinib shows that median PFS was 2.1 months in the placebo group[56].

Based on historic average clinical outcomes, we propose a clinical study that will be integrated by a dose finding approach followed by a randomized phase II study with PFS as the primary endpoint, designed to have 80% power for a two-sided 0.05 level test. The completion of the first part of the study will require approximately 8-9 months for accrual assuming 9 to 12 patients will be required for the completion of the phase I portion with the participation of 7 institutions (Georgetown Lombardi comprehensive Cancer Center, Memorial Sloan Kettering Cancer Center, University of California, Los Angeles, University of California, San Francisco, Vanderbilt University, Hackensack University Medical Center, and Walter Reed National Military Medical Center).

For the phase II portion, assuming a median PFS of 2 months following completion of first-line therapy with a platinum-based chemotherapy for ES-SCLC in the control arm, and an expected median PFS of 5 months for the maintenance therapy with $^{177}\text{Lu-DOTA}^0\text{-Tyr}^3\text{-Octreotate}$ and nivolumab in the experimental arm (hazard ratio 0.4), it will be required to document 40 PFS events from a total population of 44 patients enrolled during a period of 18 month, including a minimum follow up of 10 months, with an expected accrual rate of 3-4 patients per month and the participation of 6-7 institutions. Assuming a potential 15% dropout, the total number of patients to recruit will be 52 [57-59].

After the dose finding of the phase 1 portion is concluded, the phase 2 will start. The major end of the phase I is the safety and tolerability. Activity will not be adequately assessed in the phase I portion. The total number of patients required for the whole study will be 61-64 (phase I: 9-12 patients, phase II: 52 patients).

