5.1.2 Phase II

The phase II portion will consist of patients with ES-SCLC who completed platinum based standard first-line chemotherapy (e.g. 4-6 cycles of platinum plus etoposide or irinotecan) without disease progression (responders plus stable disease) at the time of initiation of the combination therapy with $^{177}\text{Lu-DOTA}^0\text{-Tyr}^3\text{-Octreotate}$ and nivolumab. Eligible patients will then be randomly allocated in two arms: one will be treated with the combination of $^{177}\text{Lu-DOTA}^0\text{-Tyr}^3\text{-}$

Octreotate and nivolumab, and the other arm will continue be followed (observation) after completion the standard chemotherapy treatment.

Randomization:

Patients who do not receive radiotherapy after chemotherapy

- The randomization must occur within 6 weeks of the last chemotherapy cycle.
- The study treatment must start within 2 weeks from randomization, but no less than 2 weeks from last dose of chemotherapy.

Patients who receive radiotherapy (including prophylactic cranial radiation and/or thoracic radiation) after chemotherapy

- Randomization must occur at least 8 weeks after completion of radiation therapy but within 12 weeks after completion of radiation therapy.

Randomization process:

- OnCore will be used as statistical center and the randomization algorithm will be developed by the study biostatistician.
- The project management department will be the first point of contact for assessment through email.

Courses are defined as 56 days of dosing. Nivolumab will be given until progressive disease, patient withdrawal, or toxicities. For patients randomized to the observation group, cross-over at the time of disease progression will be allowed, since the primary endpoint is PFS and not OS.

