5.2 Drug Administration

5.2.1 $^{177}\text{Lu-DOTA}^0\text{-Tyr}^3\text{-Octreotate}$

$^{177}\text{Lu-DOTA}^0\text{-Tyr}^3\text{-Octreotate}$ will be administered every 8 weeks. The first dose of $^{177}\text{Lu-DOTA}^0\text{-Tyr}^3\text{-Octreotate}$ will be given two weeks after the first administration of nivolumab. Each dose is infused over 30 minutes. On the day of $^{177}\text{Lu-DOTA}^0\text{-Tyr}^3\text{-Octreotate}$ infusion, an intravenous bolus of anti-emetics will be given (suggested options: ondansetron (8 mg), granisetron (3 mg), or tropisetron (5 mg)). Administration of $^{177}\text{Lu-DOTA}^0\text{-Tyr}^3\text{-Octreotate}$ may be given one day earlier or delayed up to 1 week due to holidays, inclement weather, conflicts, or similar reasons. Prednisone should be avoided as preventive anti-emetic treatment due to potential-negative effect on anti-PD-1 therapy. In case of nausea or vomiting despite the use of aforementioned anti-emetic, patients can be treated with other anti-emetic medications at the discretion of the treating physician.

Concurrent amino acids are given with each dose of $^{177}\text{Lu-DOTA}^0\text{-Tyr}^3\text{-Octreotate}$ since co-infusion of amino acids leads to a significant reduction (47%) in the mean radiation dose to the kidneys. The amino acid solution and $^{177}\text{Lu-DOTA}^0\text{-Tyr}^3\text{-Octreotate}$ are administered in parallel by peripheral vein infusion.

Table 2. ¹⁷⁷Lu-DOTA⁰-Tyr³-Octreotate Administration Schedule.

Preparation	Starting time (h)	Infusion Rate (ml/h)	Duration (h)
Granisetron 3 mg (or alternative)	0	Bolus	-
Amino acids: 1-2.2 L solution*	0	250 to 550**	4
¹⁷⁷ Lu-DOTA ⁰ -Tyr ³ -Octreotate	0.5	50	0.5
Saline solution 25 mL – (two pump method) ¹	1	50	0.5

¹When the two-pump method is used, ¹⁷⁷Lu-DOTA⁰-Tyr³-Octreotate is pumped directly into the infusion line. The infusion line must be flushed with at least 25 ml of sodium chloride 9 mg/ml (0.9%) solution for injection after the infusion of ¹⁷⁷Lu-DOTA⁰-Tyr³-Octreotate.

* For specifications of the recommended commercial amino acid solution for coinfusion, please refer to the investigator brochure.

** The infusion rate may be reduced at the discretion of the investigator.

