11.3 Data Analyses Plans

PFS will be defined as the time from random assignment to disease progression or death from any cause, whichever comes first. OS will be defined as the time from random assignment to death from any cause; living patients will be censored at the date of last follow-up. Survival will be estimated and plotted by the Kaplan–Meier method. In addition, the median progression-free and overall survival times will be reported along with the 95% confidence intervals. The cox proportional hazards regression model will be used to obtain hazard ratios (HRs) and the log-rank test will be utilized to compare survival estimates between the maintenance group and the control observation group. Secondary endpoints will be analyzed when the required number of events for the primary endpoint (PFS) has been met. The DCR is defined as the proportion of patients with a best overall response of CR, PR, or SD. The ORR is defined as the proportion of patients with a best overall response of CR or PR. All randomized subjects will consist of the safety population. This population will be used for all summaries of safety data (AEs, concomitant medications, laboratory data). P-values less than 0.05 will be considered significant. All statistical analyses will be performed using SAS (Version 9.4; SAS Institute, Cary, NC). [name] will serve as the study statistician.

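### The phase II sizing makes no allowance for the permitted lag of up to 2 weeks between randomization and first dose; show it as a sensitivity range beside the 80%, and shorten it by randomizing just before C1D1

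*Combined protocol and SAP*

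**What the plan says.** **Sizing (11.2).** The comparison is "designed to have 80% power for a two-sided 0.05 level test". The control figure is given by "assuming a median PFS of 2 months following completion of first-line therapy with a platinum-based chemotherapy". The experimental figure is "an expected median PFS of 5 months for the maintenance therapy with" the combination. The text continues "hazard ratio 0.4), it will be required to document 40 PFS events from a total population of 44 patients", and 52 are to be recruited to cover 15% dropout.

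**Endpoint (7.1.6 and 11.3).** Both sections start the clock at randomization: "PFS will be defined as the time from random assignment to disease progression or death from any cause".

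**Start of treatment (4.2.1.5 and 5.1.2).** For patients without radiotherapy after chemotherapy: "The study treatment must start within 2 weeks from randomization, but no less than 2 weeks from last dose of chemotherapy". For patients who do have radiotherapy, these sections date randomization from the end of radiotherapy but give no limit from randomization to first dose.

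**Order of the two drugs (5.2.1).** The radionuclide "will be given two weeks after the first administration of nivolumab", so C1D1 is a nivolumab visit.

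**Scans (6.2 and Appendix D).** Both arms are imaged every 8 weeks. The study calendar ties the first on-treatment assessment to C2D1. The starting point of the observation arm's scan schedule is not stated.

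**The concern.** The event count treats the hazard ratio of 0.4 as present from the moment of randomization. Under the plan's own timing rules, a combination patient can be untreated for up to 2 weeks after that moment. A patient randomized soon after the last chemotherapy dose must wait, because treatment may not begin within 2 weeks of that dose.

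With a 2-month control median, 2 weeks is a noticeable part of the time at risk. Progressions and deaths before first dose count towards the 40 events. They carry no treatment contrast, and they pull the log-rank statistic and the Cox hazard ratio towards no difference. The 40 events leave little margin over 80%.

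The lag can also separate the scan dates of the two arms, if combination scans follow C1D1 and observation scans follow randomization.

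**Working it through.** **Inputs.** Medians of 2 and 5 months, hazard ratio 0.4, 40 events, 44 patients, two-sided 0.05, 15% dropout (11.2); lag of at most 2 weeks, or 0.46 month (4.2.1.5, 5.1.2). Assumed here, because the plan does not state them: 1:1 allocation and exponential hazards.

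**1. The plan's own figure, no lag.**
- Hazard ratio: 2/5 = 0.4.
- Events by Schoenfeld: 4 × (1.960 + 0.842)² / (ln 0.4)² = 37.4, so 38. Freedman's formula gives 43. The stated 40 lies between them.
- Power at 40 events by Schoenfeld: Φ(√40/2 × ln 2.5 − 1.96) = Φ(0.94) = 82.6%.
- Power at 40 events by Freedman: Φ(√40 × 0.6/1.4 − 1.96) = Φ(0.75) = 77.4%.
- Log-rank simulation (22 per arm, analysis at event 40): 80%.
- Dropout: 44/0.85 = 51.8, so 52.

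The stated design reproduces.

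**2. The different wording of the two medians.** Under a constant hazard, a patient who is progression-free at randomization still has a 2-month median from that point. Re-dating the control figure from the end of chemotherapy therefore leaves power unchanged. Subtracting the elapsed gap from the 2 months would raise power (97% at a control median of 1.5 months). The wording alone costs nothing.

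**3. Size of the lag.** At the control hazard, 1 − 2^(−0.46/2) = 14.7% of patients progress or die within 2 weeks.

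**4. Reading A: control hazard until first dose, hazard ratio 0.4 afterwards.** If everyone waits 2 weeks, the combination median from randomization is 0.46 + (0.693 − 0.159)/0.1386 = 4.31 months. Simulated power at 40 events:

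| Start of treatment | Power |
|---|---|
| No lag | 80% |
| Spread evenly over 0-2 weeks | about 72% |
| All at 1 week | 71-73% |
| All at 2 weeks | about 64% (63-64%) |

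The accrual wording, "enrolled during a period of 18 month, including a minimum follow up of 10 months", can be read in more than one way. Accrual over 8, 12.6 or 18 months gives nearly the same results.

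**5. Reading B: control hazard until first dose, but the 5 months counted from randomization.** The hazard after first dose must then be (0.693 − 0.159)/(5 − 0.46) = 0.118 per month. Divided by the control hazard of 0.347, that is a hazard ratio of 0.34 for a 2-week lag; the same step gives 0.37 for 1 week. Power is about 77-79% over these lags (separate simulation runs differ by about a point).

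**6. Reading C: 5 months counted from first dose and no progression during the wait.** Power is 85% for a 1-week lag and 88-89% for 2 weeks. This reading gives the waiting combination patients no risk, although the sizing gives observed patients a 2-month median.

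**7. Scan timing.** Under reading A with a 2-week lag, and with progression found only at 8-weekly scans, power is 65% if both arms share one scan grid. It is 84% if combination scans run from C1D1 and observation scans from randomization. The rise comes from later assessment in one arm and is not a treatment benefit.

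**The case against.** **A reader might infer that the trial really has 60-73% power, not 80%.** The documents do not support that. The figure belongs to reading A only. Two weeks is a ceiling, and nothing suggests that every patient would start on the last permitted day. The 5-month figure names a regimen and an arm and gives no starting point. Since PFS is defined from randomization, the natural reading is an arm-level median with any lag already inside it, and the loss is then only a few points.

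**A reader might also infer that the two medians, worded on different clocks, lower power by themselves.** Step 2 shows that they do not under the constant hazard used in the sizing.

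**A still stronger inference is that the effect begins only with the radionuclide, 2 weeks after nivolumab.** That would put power near 46% if every patient had a 4-week gap. It requires nivolumab to do nothing in its first 2 weeks, whereas the précis reports activity of nivolumab alone in this disease.

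The best argument on the other side is that there is no arithmetic error and that the documents settle neither the size nor, once scan timing is considered, the direction of the change. That stands. It does not remove the omission: the lag is permitted, 11.2 is silent on it, and the scan schedule of the observation arm has no stated anchor.

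**Conclusion.** The concern holds as a cheap improvement to the plan, not as a power defect. PFS starts at randomization, the combination may start up to 2 weeks later (the limit is listed only for patients without radiotherapy after chemotherapy), and the sizing applies the hazard ratio of 0.4 from time zero.

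The 80% is right for the no-lag case. Allowing for the lag, power runs from about 80% down to about 64% if there is no effect before first dose and 0.4 afterwards, with 72% for an even spread. It is about 77-79% if the 5 months is counted from randomization. All of these rest on 1:1 allocation, exponential hazards and analysis at the 40th event. The real distribution of start times is unknown, so no single figure should replace the 80%.

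**What to change.** - **4.2.1.5 and 5.1.2:** randomize a patient only once the first combination visit is booked, so that randomization falls just before the planned C1D1 in both arms. This moves the randomization date and leaves the treatment schedule as written. It removes most of the untreated time and most of the possible shift in scan dates between arms.
- **11.2:** state that both medians are measured from randomization. Beside the 80%, report power at 40 events over a 0-2 week start lag as a sensitivity range, with its assumptions.
- **Analysis:** keep the log-rank test on all patients as randomized, with PFS from randomization.

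Cost: wording in three sections, with no extra patients or procedures. Sites must book a visit before allocation is known, and the slots of patients allocated to observation (about half under 1:1) will be released. Because the calendar gives only nivolumab on C1D1, a released slot is a nivolumab infusion slot.
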